Data will be summarized by group and in total. In summary tables of continuous variables, the minimum, maximum, mean, and standard deviation will be presented with one decimal place. We will use counts and percentages in table for categorical variables. The denominator for each percentage will be the number of participants within the group unless otherwise specified. All hypothesis testing will be carried out at a two-tailed Type I error rate of $\alpha = .05$ unless otherwise specified. P-values will be rounded to three decimal places with a minimum of < 0.001 in tables. If statistical methods change during analysis, this will be documented in all reports with justification. Additional analyses of these data will be inevitable, but any exploratory analyses will be clearly marked as such.

Statistical power analysis and sample size selection

IRT and DIF analyses require large samples due to the large number of free parameters to be estimated. The proposed sample size herein is larger than other successful implementations of these same analyses carried out in other IRT studies.¹⁶⁻¹⁹ Moreover, we have carried out computer simulations to determine if our proposed sample sizes will be sufficient to create IRT models. We assumed a one-factor model across two groups at $n = 100$ each with standardized factor loadings set to .7 for eight questionnaire items. We used two groups for this simulation to ensure that any pairwise model comparisons would have adequate power. For this simulation, we specified that a non-significant model χ^2 was a good fit, which is a conservative decision because this particular test is highly sensitive relative to other measures of model fit, especially with large samples. Across 500 iterations, a good-fitting model was identified across groups 90% of the time. Even dropping the sample size to as low as $n = 50$ would identify a good-fitting model 84% of the time.

Missing data

We will describe the rate of missing data on an item-by-item basis using frequency tables in R. We do not anticipate high rates of missing data, but we will conduct subgroup analyses by health literacy, site, and administration mode as need to help diagnose any problems with missing data. For DIF analyses, IRT models

Table 1	
Visit 1 (Baseline)	Description of instrument
Language Assessment	To determine testing in English or Spanish
Single Item Health Literacy Screener	To screen for possible literacy status

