This analysis will have several limitations. 1. The sample may not be generalizable as it was restricted to urban and English- or Spanish-speaking participants who consented to participation in a research study. 2. This is a baseline analysis that does not take into the account the potential for changing views on vaccination in the setting of an ongoing pandemic and public health education campaigns. We plan longitudinal analyses in the future to address this limitation. 3. Although we have hypothesized a causal pathway that includes race/ethnicity and health literacy as a partial mediator, we are unable to evaluate alternative pathways for factors that were not measured as part of this study. 4. Mediator-outcome confounding or collider bias is a possibility in this analysis in reference to the variable, educational level, which is related to health literacy and potentially related to the outcome of vaccine confidence. 5. In addition, the possibility of measurement error in the assessment of health literacy not only affects the estimate of health literacy's relationship with vaccine confidence, but also the estimate of the relationship of race or ethnicity with VCI.

Despite these limitations, we feel this analysis adds to the available knowledge on vaccine confidence during the COVID-19 pandemic and opportunities to improve public uptake of vaccination through targeted campaigns and interventions.

Cognitive Correlates of Rumination

Version notes. This plan was added in Version 4.2, 02 June 2021. At the time of the plan, adjust MOCA-B scores had been examined for distributional characteristics and differential item functioning for depression items (DIF; i.e., different measurement properties for PHQ-9 and PROMIS Depression by high-low MOCA-B). Some other analyses of rumination and depression had also been carried out as described in the above section *Prediction of depression: Health literacy as a moderator of rumination, pain, fatigue, and sleep disturbance*.

Sample. The sample will contain all participants ($N = 478$) who completed cognitive measures (see below) recruited into the parent health literacy study before recruitment was stopped due to the COVID-19 pandemic (March 2021). The cognitive measures were administered at one of three time points in the study; corresponding rumination and PROMIS depression measures will be used from the same time point.

Overarching goal

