Mean centering. Because we plan to test interaction effects (i.e., moderation), we will mean-center brooding, reflection, PROMIS depression, age, and Health LITT. If any additional continuous covariates are used in exploratory analyses, these will also be centered around the mean.

Exploratory Structural Equation Modelling

All items in the cognition measures (as latent variables) and brooding and reflection (as scores) will be included (see above). Based on the parallel analysis to determine the number of factors, multiple exploratory factors from

the cognitive measures will be regressed on our two covariates of interest – brooding and reflection. We anticipate that brooding and reflection will be inversely related with cognition, in particular items related to memory and executive function. In other words, higher levels of rumination will be associated with lower levels of cognition.

We will conduct these analyses using Mplus. We will report all fit indices, unstandardized associations among variables, corresponding SEs, and significance tests at a Type I error rate of .05.

Scoring rumination

Rumination will be measured using the Ruminative Responses Scale (RRS) short form, a 10-item form that includes two subscales, brooding and reflection. The RRS uses a four-point response scale for each item with a total score derived from the sum of the individual items. Higher scores indicate higher levels of rumination. All variables will be examined in a continuous manner, rather than using cut scores. If 80% or more of the items are present, we will score the subscale using prorating.

Hypotheses and testable predictions

We hypothesize that rumination will have a significant association with cognition. Specifically, higher scores in both domains of rumination (brooding and reflection) will be related to lower scores on cognitive factors. Overall, we expect cognition to be more strongly related to brooding than reflection. In past work ([name] & Raes, 2014), we found that the brooding factor was more robust than the reflection factor. Thus, it is possible that the more reliable brooding scale will have larger associations with cognition. However, the literature contains mixed findings with regard to the relative contributions of brooding versus reflection (e.g.,^{57, 58}).

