(dependent variables) on brooding, reflection, depression, and the two product terms (depression \times brooding, depression \times reflection); depression will be the moderator. The statistical significance of these two product terms will be evaluated at .05 and effect sizes will be reported. We will then conduct addition moderation analyses with age, gender, and language in the same fashion as described above. Depending on the results, moderation will be summarized using simple-slope analyses and visualization.

Other Approaches (Exploratory)

We will explore these associations in other software (e.g., lavaan, mirt)^{59, 60} for consistency across software. Supplementary results will be made available in an open-science repository.

Backup plan for factor analyses. If we have difficulty identifying latent variable models, we will reframe the analyses of cognition around general levels of cognition using the MoCA-B total score.

Factor analysis of the Ruminative Responses Scale (RRS);

Added 26 January 2023

Although the RRS is commonly organized into two factors – brooding and reflection – some literature has failed to support this two-factor structure.⁶¹ To clarify the structure of the RRS, we will randomly divide our baseline sample into an exploratory and confirmatory half, and then conduct exploratory and confirmatory factor analyses. To determine the number of factors, we will use primarily parallel analysis as implemented in the *psych* package, specifying that the items are ordered categories. Secondarily, we will also examine parallel analysis as implemented in the *nFactors* package and the method of Lubbe (2019).⁵⁶

Based on previous literature, we anticipate that a one- or two-factor model will be a good fit to the RRS, but we will be guided by parallel analysis. Although factor loadings are continuous, we will flag any factor loading greater than or equal to 0.3 as an indicator of the factor. For the factor analyses, we will use the *mirt* package using a graded response model for ordered categories. We will explore different factor rotations, although we anticipate that an oblique solution will be most appropriate, such as the *geominQ* rotation that allows for factors to be correlated.

For validity of any factor solutions, we will correlate the RRS factors with depression (i.e., PROMIS Depression and PHQ-9) and expect statistically significant associations.

Other Interim and Exploratory Analyses

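### In the main rumination-cognition model, mutually adjusted brooding and reflection coefficients do not test whether both domains are inversely related to cognition, and no joint test covers the overall association

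*SAP*

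**What the plan says.** The sample is "all participants ($N = 478$) who completed cognitive measures" (SAP, Cognitive Correlates of Rumination, Sample). Under Hypotheses and testable predictions there are three statements:

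- an overall one: "We hypothesize that rumination will have a significant association with cognition";
- one about each domain: "higher scores in both domains of rumination (brooding and reflection) will be related to lower scores on cognitive factors";
- an ordering: "Overall, we expect cognition to be more strongly related to brooding than reflection".

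Under Exploratory Structural Equation Modelling (ESEM), factors from "the cognitive measures will be regressed on our two covariates of interest", namely brooding and reflection, in one model. The output is fit indices, associations, standard errors and "significance tests at a Type I error rate of .05". The Overview under Statistical methodology makes testing two-tailed.

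Scoring rumination describes a total score from the 10-item form, but no test of that total against cognition is planned. Supplementary analyses provides for separate regressions by cognitive factor and by subscale, to be used if the ESEM is hard to identify. That paragraph anticipates three cognitive factors and two subscales, and counts three models.

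A later section, Factor analysis of the Ruminative Responses Scale (added January 2023), notes that "some literature has failed to support this two-factor structure", anticipates one or two factors and expects an oblique rotation.

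**The concern.** Neither the overall statement nor the two-domain statement is conditional on the other domain. A reader takes them as claims about rumination as a whole and about each subscale on its own. The ESEM coefficients answer something narrower: what brooding adds once reflection is known, and the reverse.

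The two questions differ to the extent that the subscales overlap. Both come from one short form, and the SAP's own later text doubts that they separate cleanly. With overlap, a shared association is divided between two less precise coefficients. Two consequences follow:

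- The two-domain prediction can fail in the output although each subscale is inversely related to cognition.
- The overall association has no test of its own. The plan does not say which pattern of coefficients, over how many factors, would count as support.

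**Working it through.** The SAP gives no power, effect size or subscale correlation for this analysis, so there is no figure of its own to reproduce.

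**Inputs from the SAP.** N = 478; two-sided alpha = .05 per coefficient; both subscales in one model; brooding expected to be the stronger correlate.

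**Assumed inputs.** Correlation of brooding (r1) and of reflection (r2) with one cognitive factor; brooding-reflection correlation rho = .5, .6 and .7. The factor is treated as observed. With a latent factor, power would be somewhat lower.

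**Formulas.**

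- Adjusted coefficient (standardised): b1 = (r1 - rho·r2)/(1 - rho²), and likewise b2.
- R² = b1·r1 + b2·r2.
- SE = sqrt[(1 - R²)/((N - 3)(1 - rho²))].
- The two estimates have sampling correlation -rho. The chance that both, or at least one, is significant comes from simulating that bivariate distribution.
- Joint test: F with 2 and N - 3 df, noncentrality N·R²/(1 - R²).
- One subscale alone: t test of a correlation, N - 2 df.

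**Worked case, r1 = r2 = -.20, rho = .6.** b = (-.20 + .12)/.64 = -.125. R² = 2 × .125 × .20 = .05. SE = sqrt(.95/(475 × .64)) = sqrt(.95/304) = .056. The ratio is 2.24, so power is 61% per coefficient. Both are significant and negative in 28% of studies. One subscale alone: .20/sqrt(.96/476) = 4.45, power 99%.

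**Results per cognitive factor; the three values are for rho = .5, .6, .7.**

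| r1 / r2 | Both adjusted significant and negative | Each alone (brooding; reflection) | At least one adjusted significant | Joint 2-df test |
|---|---|---|---|---|
| -.20 / -.20 | 49%, 28%, 9% | 99%; 99% | 98%, 94%, 84% | above 99% |
| -.20 / -.12 | 6%, 1.5%, 0.1% | 99%; 75% | 96%, 95%, 95% | about 98% |
| -.15 / -.12 | 7%, 2%, 0.3% | 91%; 75% | 76%, 68%, 59% | 89%, 87%, 86% |
| -.12 / -.12 | 5%, 1%, 0.2% | 75%; 75% | 61%, 50%, 39% | 78%, 76%, 73% |

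**Sign of the reflection coefficient.** It is zero or positive whenever |r2| ≤ rho·|r1|. With -.20/-.12:

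- rho = .5: (-.12 + .10)/.75 = -.03
- rho = .6: (-.12 + .12)/.64 = 0.00
- rho = .7: (-.12 + .14)/.51 = +.04

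With -.15/-.10 the true value is near zero, and the estimate is positive in 26%, 39% and 56% of studies.

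**Several factors.** With the three anticipated factors, six coefficients are tested at .05. If any one may count as support, the chance of at least one false positive under the null is 1 - .95⁶ = 26.5% if the tests are independent. A simulation with an assumed factor correlation of .5 gives about 21%.

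**The case against.** **The main analysis is said to miss real associations often.** A reader might infer this, but the documents do not support it. They give neither an effect size nor a subscale correlation. For the overall hypothesis the fair comparison with a joint test is at least one significant coefficient, not the power of each. On that basis the gap almost closes when brooding is clearly stronger (-.20/-.12). At -.30 for both domains, at least one coefficient is almost always significant (99.9% or more). Looking across three factors makes a complete miss rarer still: 3% to 14% at -.15 for both, with rho .5 to .7 and factor correlation .5. What stands is conditional. When both associations are small, misses persist even with brooding modestly ahead (-.15/-.12), and the multi-factor reading lowers misses only by leaving false positives uncontrolled.

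**Separate subscale models are planned.** True, so it would be wrong to say that the section contains none. They are conditional on the ESEM failing, however, so if the ESEM works they are not run.

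**Mutual adjustment is legitimate.** Also true. The SAP is interested in the relative contributions of the two domains and disclaims causal inference. A sign change after adjustment answers a different question and is not an error. This supports keeping the adjusted coefficients, but not using them as the test of the two-domain statement.

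**The hypothesis would be reported as unsupported or refuted.** The plan does not say so, because it states no decision rule. The fair criticism is that the rule is missing.

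**The evidence for overlap is indirect.** The remark about factor structure was written later, for another analysis, and gives no correlation. The amount of shared variance is therefore an assumption here.

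**Conclusion.** The concern holds for the main ESEM. Its strongest part is the two-domain hypothesis. Even at -.20 for both domains, where either subscale alone would almost certainly be detected, both adjusted coefficients reach significance in half of studies at best over rho .5 to .7. In the pattern the SAP predicts, with brooding stronger, reflection's coefficient can vanish or change sign although reflection alone is inversely related. At -.30 for both the problem is much smaller: both are significant in 96%, 87% and 65%.

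For the overall hypothesis the loss is limited to small associations of similar size. At -.12 for both, at least one coefficient is significant in 61% to 39% of studies, against 78% to 73% for a joint test.

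All figures are per cognitive factor and rest on assumed correlations. This is a secondary, associative analysis outside the primary differential item functioning work. The point should be addressed, but it does not affect the study's main conclusions.

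**What to change.** In Exploratory Structural Equation Modelling and Hypotheses and testable predictions:

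1. Test the overall hypothesis by a joint Wald test that the brooding and reflection paths are all zero, first across all cognitive factors and then for each factor. The test across factors does not depend on the rotation chosen.
2. Judge the two-domain hypothesis from two ESEMs with one subscale each, keeping the same number of factors and the same rotation. State which factors must show the inverse association.
3. Keep the mutually adjusted coefficients as each domain's unique contribution, reported with the brooding-reflection correlation.
4. In Supplementary analyses, reconcile the fallback count: three factors by two subscales is six models, not three.

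The cost is SAP wording, one joint-test statement, two extra Mplus runs on existing data and a few more estimates to report. If this analysis has already been run, the additions should be labelled as post hoc, in line with the SAP's own rule for analyses that were not pre-registered.

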(dependent variables) on brooding, reflection, depression, and the two product terms (depression \times brooding, depression \times reflection); depression will be the moderator. The statistical significance of these two product terms will be evaluated at .05 and effect sizes will be reported. We will then conduct addition moderation analyses with age, gender, and language in the same fashion as described above. Depending on the results, moderation will be summarized using simple-slope analyses and visualization.

Other Approaches (Exploratory)

We will explore these associations in other software (e.g., lavaan, mirt)^{59, 60} for consistency across software. Supplementary results will be made available in an open-science repository.

Backup plan for factor analyses. If we have difficulty identifying latent variable models, we will reframe the analyses of cognition around general levels of cognition using the MoCA-B total score.

Factor analysis of the Ruminative Responses Scale (RRS);

Added 26 January 2023

Although the RRS is commonly organized into two factors – brooding and reflection – some literature has failed to support this two-factor structure.⁶¹ To clarify the structure of the RRS, we will randomly divide our baseline sample into an exploratory and confirmatory half, and then conduct exploratory and confirmatory factor analyses. To determine the number of factors, we will use primarily parallel analysis as implemented in the *psych* package, specifying that the items are ordered categories. Secondarily, we will also examine parallel analysis as implemented in the *nFactors* package and the method of Lubbe (2019).⁵⁶

Based on previous literature, we anticipate that a one- or two-factor model will be a good fit to the RRS, but we will be guided by parallel analysis. Although factor loadings are continuous, we will flag any factor loading greater than or equal to 0.3 as an indicator of the factor. For the factor analyses, we will use the *mirt* package using a graded response model for ordered categories. We will explore different factor rotations, although we anticipate that an oblique solution will be most appropriate, such as the *geominQ* rotation that allows for factors to be correlated.

For validity of any factor solutions, we will correlate the RRS factors with depression (i.e., PROMIS Depression and PHQ-9) and expect statistically significant associations.

Other Interim and Exploratory Analyses

Differential Item Functioning of Depression by Cognitive Ability (MoCA-B)

With funding from a National Institute on Aging (NIA) Supplement, we have collected data on the Montreal Cognitive Assessment Test – Basic (MoCA-B). Data from the current project provide an opportunity for preliminary data for an upcoming grant proposal on the relationship between cognitive function and health-related quality of life. Thus, we will conduct DIF analyses of the depression scale of the PROMIS Profile and the PHQ-9 using high vs. low scorers on the MoCA-B as determined by a median split. The procedures of the DIF analyses will be the same as described above. We will also conduct visual analysis of the relationship between the MoCA-B and depression using the *ggplot2* package of R, as well as quantify the associations among these scales using Pearson correlations along with 95% CIs.

These analyses will be interim, before all data have been collected, as they will be needed for a grant submission in June of 2020. The results of this interim analysis will not affect any planned hypotheses presented elsewhere in this plan. The data analyzed for this interim analysis will be all data collected before 01 March 2020.

Health Literacy as a Possible Mediator Between Demographics and Symptoms Related to Stress and Trauma: An Application Of The Paasche-Orlow & Wolf Model

Added 02 October 2024 for Version 5.1

Health literacy has been highlighted as a barrier to service utilization and thus significantly impacts disease outcomes⁶². Outcomes may be impacted by an individual's difficulty with proper medication dosage or lack of trust in the healthcare system, as examples^{63, 64}. Both physical and mental health outcomes are important, including mental health symptoms related to stress and trauma, which people with low health literacy may experience at a high frequency. Although health literacy can be linked to mental health conditions such as depression, less is known about its connection to trauma-related symptoms. To address this gap, this study will identify the impact of health literacy on trauma-related symptoms as measured by the PCL-5. We will also explore the association between the PCL-5 and health-related quality of life measured by the PROMIS Profile.

Aims:

1. Determine the association between health literacy and symptoms related to stress and trauma measured by the PCL-5 scale, while controlling for demographic variables. Language can be explored as a moderator.
2. Determine whether health literacy mediates the relationship between baseline demographics (e.g., education, age, gender) and future stress-related symptoms using the PCL-5. Will run separate models for English and Spanish.
3. Determine which aspects of health-related quality of life (measured by PROMIS-57 Profile v2.1, which includes Physical Function, Anxiety, Depression, Fatigue, Sleep Disturbance, Ability to Participate in Social Roles and Activities, Pain interference, and Pain Intensity) are associated with trauma symptoms measured by the PCL-5, after statistically controlling for demographics and health literacy.

Hypotheses:

1. There will be a significant association between health literacy (measured by Health LiTT) and the PCL-5 scale, such that lower health literacy will be associated with higher trauma-related symptoms.
2. Health literacy serves as a mediator between baseline demographics (education, age, gender, ethnicity) and future stress related symptoms as per the PCL-5.
3. Higher levels of self-reported anxiety, depression, and ability to participate in social roles and activities from the PROMIS-57 will be associated with higher PCL scores.

Data Description

Datasets used

NIH-funded Reducing Assessment Barriers for Patients with Low Health Literacy dataset, also known as the DIF study (PI: [name]). All timepoints will be analyzed for this project (baseline, 3-month, and 6-month time points). The dataset is not publicly available. The data are not public, but will be made available to us from the DIF team at the time of publication.

Data Collection Procedures (from parent study)

Participants included those who were aged 18 or older, could provide informed consent, were open to randomization for mode of administration, were willing to complete questionnaires, fluent in English and/or Spanish, willing to attend three face-to-face sessions, and did not have plans to move outside of the study area for six months. Study participants were recruited from two sites: Northwestern University (Chicago, IL) and Boston Medical Center (Boston, MA). Participants were ineligible for the study if they had significant cognitive

or neurologic impairment, were imprisoned or detained, could not consent, had inadequate vision (to see study materials), and had inadequate hearing or manual dexterity to use electronic tablets. All participants provided demographic data and completed three measures of health literacy including the Health LiTT test, Single Item Literacy Screener (SILS), and the Numeracy Understanding in Medicine Instrument (NUMi). They also completed the PCL-5 and PROMIS-57 profile. Participants completed interviews three months apart (baseline, 3-month, and 6-month visits).

Codebook

Available from REDCap study profile.

Analysis Plan

Aim 1 example code:

```
